Clinical Trial Protocol

Document Number:		c22193484-01
EudraCT No.	2018-003103-19	
BI Trial No.	1407-0033	
BI Investigational Medicinal Product	BI 730357	
Title	Investigation of pharmacokinetics and absolute oral bioavailability of BI 730357 administered as an oral dose with an intravenous microtracer dose of BI 730357 BS (C-14) in healthy male volunteers	
Lay Title	A study in healthy men to measure the amount of BI 730357 in the blood when taken as a tablet	
Clinical Phase	I	
Clinical Trial Leader	
Phone: Fax:
	
Principal Investigator	
Phone: Fax:
	
Status	Final Protocol	
Version and Date	Version: 1.0	Date: 29 Nov 2018
Page 1 of 64		

Proprietary confidential information © 2018 Boehringer Ingelheim International GmbH or one or more of its affiliated companies. All rights reserved. This document may not - in full or in part - be passed on, reproduced, published or otherwise used without prior written permission
		

Proprietary confidential information © 2018 Boehringer Ingelheim International GmbH or one or more of its affiliated companies

CLINICAL TRIAL PROTOCOL SYNOPSIS

Company name	Boehringer Ingelheim
Protocol date	29 Nov 2018
Revision date	Not applicable
BI trial number	1407-0033
Title of trial	Investigation of pharmacokinetics and absolute oral bioavailability of BI 730357 administered as an oral dose with an intravenous microtracer dose of BI 730357 BS (C-14) in healthy male volunteers
Principal Investigator:	
Trial site	
Clinical phase	I
Trial rationale	This trial is intended to examine the absolute oral bioavailability of BI 730357 as tablet formulation for oral administration. The data are considered necessary to further understand the pharmacokinetics of BI 730357.
Trial objective	To determine the absolute oral bioavailability of BI 730357 after administration of 50 mg BI 730357 as tablet and 100 µg BI 730357 BS (C-14) as intravenous microtracer
Trial design	Non-randomized, open-label, single period, single arm design
Trial endpoints:	Primary endpoints: AUC _{0-∞} [C-14]BI 730357 BS (after i.v. administration) AUC _{0-∞} BI 730357 (after p.o. administration) Secondary endpoints: None defined.
Number of subjects total entered each treatment	6 * 6 * * In case a subject vomits within 12 hours after administration of 50 mg BI 730357 as tablet on Day 1 or a subject drops out for other reasons, an additional subject may be entered and dosed in order to ensure at least 6 subjects completed the trial as per protocol. Thus, as up to 2 additional subjects may be entered, the actual number of subjects entered may increase up to a maximum of 8 subjects.
Diagnosis	Not applicable

Proprietary confidential information © 2018 Boehringer Ingelheim International GmbH or one or more of its affiliated companies

Main criteria for inclusion	Healthy male subjects, age of 18 to 65 years (inclusive), body mass index (BMI) of 18.5 to 29.9 kg/m ² (inclusive)
Test product 1 (T) dose mode of admin.	BI 730357 film-coated tablet (test treatment T) 50 mg Oral with 240 mL of water after an overnight fast of at least 10 h
Test product 2 (R) dose mode of admin.	BI 730357 BS (C-14) as intravenous solution (reference treatment R) 100 µg infusion consisting of 98.0 µg unlabelled BI 730357 mixed with 2.0 µg labelled [C-14]BI 730357 BS in 10 mL i.v. solution (10 µg BI 730357 BS (C-14) / mL) The radioactive dose per infusion has been calculated to not exceed 0.3 µCi = 0.01 MBq. Intravenous infusion of 15 min starting at 1.25 hours (i.e. around t _{max}) after an orally administered dose of 50 mg BI 730357 (as tablet)
Duration of treatment	Oral dose (test treatment T): Single oral dose, Day 1 Intravenous dose (reference treatment R): Single i.v. infusion of microtracer dose over 15 min, Day 1
Statistical methods	Absolute bioavailability (F) will be estimated by the ratio of the geometric means (test treatment T / reference treatment R) for the primary endpoints (dose normalized) AUC _{0-∞} . Additionally, their two-sided 90% confidence intervals (CIs) will be provided. This method corresponds to the two one-sided t-tests procedure, each at the 5 % significance level. Since the main focus is on estimation and not testing, an acceptance range was not specified. The statistical model will be an ANOVA on the logarithmic scale including the fixed effect for 'formulation' and 'subject' as a random effect. CIs will be calculated based on the residual error from ANOVA. Descriptive statistics will be calculated for all endpoints.

Proprietary confidential information © 2018 Boehringer Ingelheim International GmbH or one or more of its affiliated companies

FLOW CHART

Visit	Day	Planned time (relative to first drug administration) [h:min]	Approximate clock time of actual day [h:min]	Event and comment	Safety laboratory	PK plasma BI 730357	PK plasma [C-14]BI 730357 BS	12-lead ECG	Vital signs (BP, PR)	Local tolerability assessment	Questioning for AEs and concomitant therapy ⁷
1	-21 to -2			Screening (SCR) ¹	x						
2	-1	-18:00	14:00	Admission to trial site	x ⁵			x	x		
		-14:00	18:00	Dinner							
		-10:30	21:30	Light supper (voluntary) ⁸							
	1	-2:00	06:00			x ^{2,3}	x ³	x ³	x ³		
		0:00	08:00	Drug administration (50 mg BI 730357 as tablet, oral)							
		1:00	09:00			x					
		1:15	09:15	Start of IV infusion containing BI 730357 BS (C-14)							
		1:20	09:20				x				
		1:25	09:25				x				
		1:30	09:30	Stop of IV infusion		x	x				
		1:45	09:45			x				x	
		2:00	10:00	240 mL fluid intake		x	x	x			
		2:30	10:30			x	x				
		3:30	11:30			x	x				
		4:00	12:00	240 mL fluid intake				x	x		
		5:00	13:00	Lunch ⁴		x	x				
		7:00	15:00			x	x				
		11:00	19:00	Dinner							
		12:00	20:00			x	x				
	2	24:00	08:00	Breakfast (voluntary) ⁴ , discharge from trial site	x	x	x	x	x	x	
	4	72:00	08:00	Ambulatory visit ⁹		x	x				
	6	120:00	08:00	Ambulatory visit ⁹	x	x	x				
	8	168:00	08:00	Ambulatory visit ⁹		x	x				
3	9 to 15			End-of-trial (EoTrial) examination ⁶	x			x	x		x

1. Subject must be informed and written informed consent obtained prior to starting any screening procedures. Screening procedures include physical examination, check of vital signs, ECG, safety laboratory (including drug screening), demographics (including determination of body height and weight, smoking status and alcohol history), relevant medical history, concomitant therapy and review of inclusion/exclusion criteria.
2. Including pharmacogenomics sample
3. The time is approximate; the procedure is to be performed and completed within 3 h prior to drug administration.
4. If several actions are indicated at the same time point, the intake of meals will be the last action.
5. Safety lab including urine drug and alcohol screening.
6. At the end-of-trial visit, the EoTrial examination includes physical examination, vital signs, ECG, safety laboratory, recording of AEs and concomitant therapies.
7. AEs and concomitant therapies will be recorded throughout the trial; during in-house days subjects will be specifically asked for twice daily.

Proprietary confidential information © 2018 Boehringer Ingelheim International GmbH or one or more of its affiliated companies

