1.4 BENEFIT - RISK ASSESSMENT

Participation in this clinical trial is without any (therapeutic) benefit for healthy subjects. Their participation, however, is of major importance for the development of BI 730357. Subjects are exposed to risks of study procedures and risks related to the exposure to the trial medication.

Procedure-related risks

The use of an indwelling venous catheter for the purpose of intravenous infusion or blood sampling may result in mild bruising, and in rare cases, in transient inflammation of the wall of the vein, or nerve injury, potentially resulting in paraesthesia, reduced sensibility, and/or pain for an indefinite period. The same risks apply for venepuncture with the purpose of blood sampling or safety laboratory assessment.

The solvent for the intravenous infusion containing a mixture of labelled and unlabelled BI 730357 is 10% PEG 400 in saline. Therefore, in case of inadvertent paravenous drug administration apart from local swelling no tissue damage is expected.

The total volume of blood withdrawn per subject during the entire study will not exceed the volume of a normal blood donation (500 mL). No health-related risk to healthy subjects is expected from withdrawal of this volume of blood.

Drug-related risks and safety measures

Although rare, a potential for drug-induced liver injury (DILI) is under constant surveillance by sponsors and regulators. Therefore, this trial requires timely detection, evaluation, and follow-up of laboratory alterations in selected liver laboratory parameters to ensure subjects' safety; see also Section [5.2.6.1.4](#), adverse events of special interest.

Risks related to oral BI 730357 administration

As the nature of the target and the mechanism of action of BI 730357 are well understood from pre-clinical studies, comparable compounds have been tested by other companies before (although not a lot of published data are available), and the animal models are believed to be predictive for the effects in humans, BI 730357 is not seen as a high-risk compound.

Single dose administration up to 400 mg BI 730357 under fasted conditions is supported by preclinical, as well as clinical safety data from first-in-human trial 1407.1, the multiple-rising-dose trial 1407-0002 and the hADME trial 1407-0031 (see Section [1.2.2](#)):

Administration of a microtracer dose of 100 µg BI 730357 BS (C-14) as infusion is expected to only marginally increase the systemic exposure to BI 730357.

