2.1.2 Primary endpoints

The following pharmacokinetic parameters will be determined in plasma for [C-14]BI 730357 BS after intravenous administration and for BI 730357 after oral administration:

- AUC_{0-∞} (area under the concentration-time curve of the analyte over the time interval from 0 to infinity)

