3. DESCRIPTION OF DESIGN AND TRIAL POPULATION

3.1 OVERALL TRIAL DESIGN AND PLAN

This Phase 1 study will be performed as a non-randomised, open-label, single period, single arm trial in healthy male subjects in order to compare the test treatment (T) to the reference treatment (R). Treatment T will be one oral tablet of 50 mg BI 730357 (intended clinical formulation (iCF)). Treatment R will be an intravenous microtracer infusion of 100 µg BI 730357 BS (C-14) consisting of 2 µg labelled [C-14]BI 730357 BS mixed with 98 µg unlabelled BI 730357 in 10 mL i.v. solution (10 µg BI 730357 BS (C-14) /mL). Both treatments will be given in the fasted state. For details, refer to Section [4.1](#).

Drug administration in treatment R will start 1.25 hours after drug administration in treatment T, i.e. at the time of the expected t_{max} of treatment T.

An overview of all relevant trial activities is provided in the [Flow Chart](#). For visit schedule and details of trial procedures at selected visits, refer to Sections [6.1](#) and [6.2](#), respectively.

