5.3 DRUG CONCENTRATION MEASUREMENTS AND PHARMACOKINETICS

5.3.1 Assessment of pharmacokinetics

For the assessment of pharmacokinetics, blood samples will be collected at the time points indicated in the [Flow Chart](#). The actual sampling times will be recorded and used for determination of pharmacokinetic parameters.

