5.3.2 Methods of sample collection

5.3.2.1 Blood sampling for pharmacokinetic analysis

For quantification of BI 730357 concentrations in plasma, 3 mL of blood will be drawn from an antecubital or forearm vein into a K₂-EDTA (dipotassium ethylenediaminetetraacetic acid)-anticoagulant blood drawing tube at the times indicated in the [Flow Chart](#).

For quantification of [C-14]BI 730357 plasma concentrations, an additional 3 mL K₂-EDTA tube will be collected as indicated in the [Flow Chart](#). Blood will be withdrawn by means of either an indwelling venous catheter or by venepuncture with a metal needle.

The EDTA-anticoagulated blood samples will be centrifuged and obtained plasma will be split into aliquots. The first aliquots should contain at least 0.5 mL of plasma. The volume of the second aliquots may be less than 0.5 mL plasma. The process from blood collection until transfer of plasma aliquots into the freezer should be completed in less than 60 min with interim storage of blood samples and aliquots on ice water. The time each aliquot was placed in the freezer will be documented. Until transfer on dry ice to the analytical laboratory, the aliquots will be stored frozen and in an upright position at about -20°C or below at the trial site. The second aliquot will be transferred to the analytical laboratory after the bioanalyst has acknowledged safe arrival of the first aliquot.

For detailed description of blood sampling, sample handling, sample preparation, sample storage, tube labelling and sample shipment refer to the laboratory manual.

At a minimum, the sample tube labels should list BI trial number, subject number, visit, and planned sampling time.

After completion of the trial, the plasma samples may be used for further methodological investigations (e.g. for stability testing or assessment of metabolites. However, only data related to the analyte and/or its metabolite(s) including anti-drug antibodies (if applicable) will be generated by these additional investigations. The study samples will be discarded after completion of the additional investigations but not later than 5 years after the CTR is archived.

Proprietary confidential information © 2018 Boehringer Ingelheim International GmbH or one or more of its affiliated companies

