7.2 NULL AND ALTERNATIVE HYPOTHESES

The absolute bioavailability of 50 mg orally administered BI 730357 compared with 2 µg of labelled [C-14]BI 730357 administered as intravenous microtracer (mixed with 98 µg unlabelled BI 730357) will be estimated by the ratio of the geometric means (test/reference) for the dose-normalized primary PK endpoints. Additionally, their 2-sided 90% confidence intervals (CIs) will be provided. This method corresponds to the two one-sided t-test procedure, each at the 5% significance level. Since the main focus is on estimation and not testing, a formal hypothesis test and associated acceptance range is not specified.

Confidence intervals have to be interpreted in the perspective of the exploratory character of the study, i.e. confidence intervals are considered as interval estimates for effects.

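### No [C-14] sample is scheduled in the 30 minutes after the infusion stops, so AUC_iv is overstated if distribution takes only minutes

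*Protocol*

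**What the plan says.** Protocol 3.1 sets the timing: "Drug administration in treatment R will start 1.25 hours after drug administration in treatment T". The infusion lasts 15 min, so it runs from 1:15 to 1:30.

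In the Flow Chart, the column "PK plasma [C-14]BI 730357 BS" is marked pre-dose and at 1:20, 1:25, 1:30, 2:00, 2:30, 3:30, 5:00, 7:00, 12:00, 24, 72, 120 and 168 h: 14 samples. The row for "Stop of IV infusion" has a mark in both PK columns. The 1:45 row is marked for unlabelled BI 730357 and for local tolerability; its [C-14] cell is empty.

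No other text adds a sample. Protocol 5.3.1 says "blood samples will be collected at the time points indicated in the" Flow Chart, and 5.3.2.1 ties the separate [C-14] tube to the same chart ("For quantification of [C-14]BI 730357 plasma concentrations, an additional 3 mL" tube).

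Protocol 2.1.2 makes the i.v. AUC a primary endpoint: "The following pharmacokinetic parameters will be determined in plasma for [C-14]BI 730357 BS after intravenous administration". The trapezoidal rule is not stated; Protocol 7.3 and SAP 7.4 refer to a sponsor procedure.

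**The concern.** If the drug distributes within minutes, the steepest part of the i.v. profile lies just after 1:30. The plan takes two samples during the 15-min infusion and none in the following 30 min, although a needle or catheter draw takes place at 1:45 anyway.

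The resulting error has a fixed sign. A sum of declining exponentials lies below both the straight line and the log-linear line joining its end points, so a single trapezoid from 1:30 to 2:00 overstates the area under either rule. This goes into AUC_iv and, taken alone, pushes F down. The 90% CI does not reflect it, because that interval is built only from the ANOVA residual error (Protocol 7.3.1).

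**Working it through.** The documents give no figure on this point, so there is none to reproduce.

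**Inputs from the documents.** Infusion duration T = 0.25 h. [C-14] times measured from infusion start: 0, 5, 10, 15, 45, 75 min and so on to 166.75 h.

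**Assumptions.** Two compartments with bolus coefficients A (fast, rate α) and B (slow, rate β). Distribution half-life 4, 5, 6, 8, 10, 12 or 15 min; A/B 5, 10, 20, 30 or 40; terminal half-life 8, 16 or 30 h. That gives 7 × 5 × 3 = 105 scenarios. The terminal slope comes from the last three points. No assay error.

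**Formulas.** Each exponential contributes C/(kT) × (1 − e^(−kT)) at the end of infusion and decays at rate k afterwards. Exact AUC = A/α + B/β. Gap error = (trapezoid over 1:30–2:00 − exact integral) / exact AUC.

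**One case by hand.** Distribution half-life 5 min, terminal half-life 16 h, 10% of AUC in the fast phase, exact AUC scaled to 1.

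- α = ln2/(5/60) = 8.318/h; β = ln2/16 = 0.04332/h; A = 0.1α, B = 0.9β, so A/B = 21.3.
- At 1:30: fast 0.4 × (1 − 2⁻³) = 0.3500; slow 3.6 × (1 − e^(−0.01083)) = 0.0388; sum 0.3888.
- At 2:00: 0.3500/64 + 0.0388 × 0.9786 = 0.0434, a nine-fold fall.
- Exact integral: (0.3500/8.318)(1 − 1/64) + (0.0388/0.04332)(1 − 0.9786) = 0.0606.
- Log trapezoid: 0.5 × (0.3888 − 0.0434)/ln(0.3888/0.0434) = 0.0788, an error of 1.82% of AUC.
- Linear trapezoid: 0.5 × (0.3888 + 0.0434)/2 = 0.1080, an error of 4.74%.
- With a 1:45 sample (0.3500/8 + 0.0388 × 0.9892 = 0.0821): log 0.0645, error 0.39%; linear 0.0746, error 1.40%.

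**All 105 scenarios, linear-up/log-down:**

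| Terminal half-life | 30 h | 16 h | 8 h |
|---|---|---|---|
| Total AUC_iv error, current grid | 0.3–1.6% | 0.5–2.7% | 0.8–4.6% |
| Median of that total | 0.6% | 0.9% | 1.5% |
| 1:30–2:00 interval alone | 0.1–1.7% | 0.2–3.0% | 0.3–5.1% |
| Interval with 1:45 added, at most | 0.3% | 0.6% | 1.0% |
| Total with 1:45 added, at most | 0.5% | 0.8% | 1.0% |
| Total with 1:25 moved to 1:45, at most (absolute) | 0.4% | 0.5% | 0.8% |

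The interval error can exceed the total because trapezoids on the concave rise during infusion understate the area slightly.

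**All-linear rule.** Total error is 6–10%, 13–19% and 16–28%, mostly from other intervals. The part that a 1:45 sample removes is 0.3–3.4, 0.5–5.8 and 0.9–9.9 percentage points.

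**Outside the grid.** At distribution half-lives of 20, 30 and 60 min the gap error is at most 0.21%, 0.09% and 0.02% (log-down) or 2.8%, 1.2% and 0.2% (linear). At 3 min with 30% of AUC in the fast phase and a terminal half-life of 8 h, it reaches 7.8% (log-down) or 20.7% (linear), and a 1:45 sample cuts this to 1.6% or 7.1%. With a single-exponential decline it is nil.

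**Effect on F.** The same disposition was run through the oral sampling times. With first-order absorption and true tmax of 1.0–1.5 h (89 scenarios), adding the tube reduced the absolute error in F in 18 of 89 (20%) under log-down; the root-mean-square error went from 1.5% to 1.6%. With zero-order input over 1.25 h, it reduced the error in all 105 (root-mean-square 6.94% to 6.15% log-down, 9.21% to 6.64% linear).

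**Scale.** The 90% CI factor for six subjects is exp(2.015 × SD × √(2/6)): 1.06, 1.12 or 1.26 at an assumed residual log-SD of 0.05, 0.10 or 0.20.

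**The case against.** The strongest counter-argument is that the trial asks for F, and no gain in F is shown. Under first-order absorption and log-down integration, the extra tube left F no better in about 80% of scenarios, because a smaller AUC_iv error no longer offsets the oral sampling error. AUC_iv on its own is only described, with no criterion attached. This stands, and it is why the point is limited to the accuracy of AUC_iv. The loss in the first-order cases is slight, however, and the zero-order cases all improve.

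Second, the size rests on assumed kinetics. The sponsor has earlier human data, and a reason for the grid may sit in text that is not public. This also stands. At a distribution half-life of 15 min the gap error is already only about 0.1–0.4% under log-down, so the effect matters only if distribution takes a few minutes, or up to about 10 min with a linear rule.

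Third, adding a point inside a convex interval must reduce that interval's error, so the improvement across scenarios mostly restates the model. That is fair. The linear-rule totals should not be read as the effect of this gap either: the large 24–72 h part falls on oral and i.v. profiles alike and partly cancels in F.

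Finally, the study is exploratory ("Confidence intervals have to be interpreted in the perspective of the exploratory character of the study"), and no passage is contradicted.

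**Conclusion.** The concern holds as a conditional one. The Flow Chart leaves the 30 min after infusion without a [C-14] sample, and for any multi-exponential decline this biases AUC_iv upwards. On the assumed grid the median total error under log-down is 0.6–1.5%, with a maximum of 4.6%; the gap contributes more under a linear rule and almost nothing if distribution is slow. Those figures depend on the assumed two-compartment kinetics, on the unstated integration rule and on error-free assays. The net effect on F can go either way. The likely error is small beside the interval from six subjects, so this is an inexpensive improvement to one primary endpoint and does not threaten the result. The Flow Chart was read from extracted text, so the 1:45 row should be checked against the original table.

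**What to change.** Either of two Flow Chart changes will do:

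- **Add** a [C-14] tube at the existing 1:45 draw. Cost: 3 mL of blood and one AMS assay per subject, so 6–8 assays and at most 8 × 3 = 24 mL over all subjects. Scheduled PK blood rises from 28 × 3 = 84 mL to 29 × 3 = 87 mL per subject; Protocol 1.4 caps all blood at 500 mL. Safety-laboratory and pharmacogenomic blood is not counted here.
- **Move** the 1:25 [C-14] sample to 1:45. The count stays at 14, with no extra blood or assay and one fewer in-infusion point.

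The sponsor can judge from its own kinetic data whether distribution is fast enough to make this worthwhile. If made by amendment, the change needs ethics committee and authority approval (Protocol 8.1). If sampling is already complete, the point applies only to later microtracer studies.

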8.5.1	Collection, storage and future use of biological samples and corresponding data	58
8.6	TRIAL MILESTONES	58
8.7	ADMINISTRATIVE STRUCTURE OF THE TRIAL	59
9.	REFERENCES	60
9.1	PUBLISHED REFERENCES.....	60
9.2	UNPUBLISHED REFERENCES.....	61
10.	APPENDICES	62
11.	DESCRIPTION OF GLOBAL AMENDMENT(S).....	63
11.1	GLOBAL AMENDMENT 1	63
11.2	GLOBAL AMENDMENT 2	63

ABBREVIATIONS

ADME	Absorption, distribution, metabolism, and excretion
AE	Adverse event
AESI	Adverse events of special interest
ALCOA	Attributable, legible, contemporaneous, original, accurate
AMS	Accelerator mass spectrometry
ANOVA	Analysis of variance
AUC _{0-∞}	Area under the concentration-time curve of the analyte in plasma over the time interval from 0 extrapolated to infinity
BA	Bioavailability
BCS	Biopharmaceutics Classification System
BI	Boehringer Ingelheim
BMI	Body mass index (weight divided by height squared)
BP	Blood pressure
BS	base
C _{max}	Maximum measured concentration of the analyte in plasma after oral administration
CA	Competent authority
CI	Confidence interval
CNS	Central nervous system
CRF	Case Report Form, paper or electronic (sometimes referred to as 'eCRF')
CRO	Contract Research Organisation
CTL	Clinical Trial Leader
CTM	Clinical Trial Manager
CTP	Clinical trial protocol
CTR	Clinical trial report
CTSU	Clinical Trial Supplies Unit

Proprietary confidential information © 2018 Boehringer Ingelheim International GmbH or one or more of its affiliated companies

DILI	Drug induced liver injury
ECG	Electrocardiogram
eCRF	Electronic case report form
eDC	Electronic data capture
EDTA	Ethylenediaminetetraacetic acid
EoTrial	End of trial
EudraCT	European Clinical Trials Database
FU	Follow-up
GCP	Good Clinical Practice
gMean	Geometric mean
hERG	Human-ether-à-go-go related gene
hLXR α	human liver X receptor α
IB	Investigator's brochure
iCF	intended clinical formulation
ICRP	International Commission on Radiological Protection
IC50	50% inhibitory concentration
IEC	Independent Ethics Committee
IPD	Important protocol deviation
IQRM	integrated quality and risk management
IRB	Institutional Review Board
ISF	Investigator site file
LC-MS/MS	Liquid chromatography with tandem mass spectrometry
MDA	Methylenedioxymethamphetamine
MDMA	Methylenedioxymethamphetamine
MedDRA	Medical Dictionary for Regulatory Activities
MRD	Multiple-rising dose
NOAEL	No observed adverse effect level
PK	Pharmacokinetic(s)
PKS	Pharmacokinetic set
PP	Polypropylene
PR	Pulse rate
QT	Time between start of the Q-wave and the end of the T-wave in an electrocardiogram
QTc	QT interval corrected for heart rate using the method of Fridericia (QTcF) or Bazett (QTcB)

Proprietary confidential information © 2018 Boehringer Ingelheim International GmbH or one or more of its affiliated companies

R	Reference treatment
REP	Residual effect period
ROR α	Retinoic acid related orphan receptor α (protein)
ROR β	Retinoic acid related orphan receptor β (protein)
ROR γ	Retinoic acid related orphan receptor γ (full length protein)
ROR γ t	Retinoic acid related orphan receptor γ t (splice variant of ROR γ protein)
SAE	Serious adverse event
SCR	Screening
SOP	Standard operating procedure
SRD	Single-rising dose
T	Test product or treatment
t_{max}	Time from (last) dosing to the maximum measured concentration of the analyte in plasma
TS	Treated set
TSAP	Trial statistical analysis plan
ULN	Upper limit of normal
XTC	Ecstasy

